## **Blinding**

Blinding of either patient or clinician was not possible. The blinding was ensured at measurement stage (data collection), in which the investigator was blinded of where MOPs were applied to either right or left by coding all digital models.

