### **Outcomes (primary and secondary) and any changes after trial commencement**

#### **Primary Outcomes**

**The** rate of tooth movement as primary outcome was determined by indirect measurement of study models and direct intraoral measurement as the following:

Alginate impressions were taken every month and study models were fabricated. The study models were then scanned with Ceramill Map 400- scanner with an accuracy of 0.02 mm (AmannGirrbach, Koblach, Austria) to obtain the three-dimensional (3D) model. By using Ceramill Mind design (CAD: computer-aided design) software (AmannGirrbach, Koblach, Austria), 3D model measurements were obtained. The baseline 3D digital model (M0) was superimposed to 3D digital models of following months (M1: 1st month, M2: 2nd month, M3: 3rd month) to determine the anteroposterior displacement of canines. The stable reference landmark used was the rugae area as recommended by other studies . To superimpose two

3D digital models, a generic visualization mesh of the following 3D model was added to the baseline model; and then performs registration of the selected reference points at rugae area (Figure 4-A,B). The best fit matching of the superimposition was evaluated by a color map with a spectrum of colors in which blue color represented the best matching while red represented the worst (Figure 4-C). From buccolingual view, the amount of canine's displacement was measured from the most middle projection from the distal surface of upper canines in baseline model to the most middle projection from the distal surface of upper canines of superimposed transparent models (M1, M2, M3) (Figure 5-A). A reference plane parallel to the bracket slots was used to ensure the standardized orientation of all measurements from buccal view (Figure 5-C). From the occlusal view, the same point was localized at the middle of the distal surface of canines to be parallel to the line of arch anterioposteriorly (Figure 5-B). Additionally, Direct measurement of distance between canine and second premolar in the patient's mouth was done every week using digital caliper (IOS, USA), from upper mesial wing of the canine bracket to upper distal wing of second premolar bracket in both right and left sides parallel to the occlusal plane for 3 months period.

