#### **Statistical analysis (primary and secondary outcomes, subgroup analyses)**

Statistical analysis was accomplished using the Statistical Package for the Social Sciences computer software (SPSS 20.0, SPSS Inc., IL, USA). Probability values equal or less than 0.05 were considered significant. Independent sample t-tests were calculated to analyze the results of the primary outcome and secondary outcomes to compare the difference between MOP and control sides. Similarly, independent sample t-test was performed to compare the amount of root resorption before and after three months in MOP and control sides separately. Chi-square was used for analysis of categorical data including the willingness to repeat the procedure and recommend it to a friend. Descriptive statistics were used to describe the satisfaction and ease of the procedure.

Reliability coefficient (Cronbach's Alpha) was used to evaluate the reliability of measurements of primary outcomes. One examiner did all measurements, and all subjects were randomly selected. Six of 3D superimposed digital models had been chosen randomly. Superimpositions on the rugae area and canine displacement were measured twice within 2-week interval. Reliability coefficient (Cronbach's Alpha) was 0.95, showing excellent superimpositions and measurement agreement.

For intraoral measurements, intra-examiner reliability was done in the lower arch after reaching 0.019x0.025 stainless steel arch wire and teeth were in a passive state; all cases were non-extraction in the lower arch. Six of subjects were selected randomly, and measurements were done twice with the 2-week interval. Measurements were done from the upper mesial wings of the lower canine bracket to the upper distal wing of the lower second premolar bracket. Reliability coefficient (Cronbach's Alpha) was 1.00, indicating excellent measurement agreement.

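### Coding alone is not shown to hide the treated side when the models are read, and at face value the model reader also measures the same mouths every week.

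*Combined protocol and SAP*

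**What the plan says.** The Blinding section states "Blinding of either patient or clinician was not possible". It claims blinding only at measurement, where "the investigator was blinded of where MOPs were applied to either right or left by coding all digital models". It does not say what the code replaced, who held it, or whether models were mirrored, cropped or read in random order.

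Under Primary Outcomes, the rate of tooth movement "was determined by indirect measurement of study models and direct intraoral measurement as the following". There are two components:
- **Model readings.** Scans are made monthly (M0 to M3) and superimposed on the palate: "The stable reference landmark used was the rugae area as recommended by other studies". Canine displacement is then read from a point located by eye on the distal surface.
- **Caliper readings.** These are taken weekly in the mouth, "in both right and left sides parallel to the occlusal plane for 3 months period".

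The reliability paragraph of the statistical section adds "One examiner did all measurements, and all subjects were randomly selected". The Interventions part says that one investigator performed the perforations. It does not say whether that person also measured.

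**The concern.** Of the two primary measurements, only the model reading has any blinding method described. Patient and clinician know the side, and nothing is said about masking the caliper reader. The model landmark is placed by eye, so a reader who knows the treated side and expects faster movement there could lean towards it without intending to.

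If the model blind is not secure, neither primary measurement is protected from expectation bias, and a report of blinded assessment would claim more than the plan supports. The reliability result does not settle this. A Cronbach's alpha of 0.95 on six re-read models shows repeatability, and a consistent lean towards one side also repeats.

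**Working it through.** No figure in the documents tests the blinding claim, so the first part sets the sections side by side. The second part is an illustration only.

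**Part 1. What the blind depends on**
1. Allocation is to right or left within each patient (Randomization section). To be blind is to not know which side was treated.
2. Left and right can be seen at reading. The models carry the palate, because superimposition uses the rugae, and the Figure 5 legend describes the measurement view as showing the upper left canines. No step that disguises side is described.
3. Seeing left and right does not reveal the treated side, which varies at random between patients. The reader must also know which side was treated in that patient and link the coded model to that patient.
4. Knowledge of the side is plausible for anyone with clinical contact. The Figure 3 legend shows three visible perforations at application, though how long they stay visible is not stated. Weekly readings for three months mean about 12 visits per mouth.
5. The link is plausible only if the model reader is also the caliper reader. The one-examiner sentence says so at face value. Its paragraph opens with the reliability of the primary-outcome measurements, which are both the model and the caliper readings, and no other text assigns them to different people.
6. If that reader recognises a dentition, the code no longer conceals the side, and nothing described in the plan prevents this.

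**Part 2. How much a small lean could matter (assumed inputs)**

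Inputs: n = 28 patients, each contributing both sides (28 is the per-group figure in the sample size section, taken here as pairs); alpha 0.05, two-sided (sidedness assumed); no true effect. The lean b and the SD of the within-patient difference are not in the documents and are assumed.

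Paired t-test: non-centrality = b × √28 / SD, 27 degrees of freedom, reject when |t| > 2.052.

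| Lean b (mm) | SD 0.3 mm | SD 0.5 mm | SD 0.7 mm |
|---|---|---|---|
| 0.05 | 0.88 → 13.6% | 0.53 → 8.0% | 0.38 → 6.5% |
| 0.10 | 1.76 → 39.8% | 1.06 → 17.5% | 0.76 → 11.3% |

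Each cell gives the non-centrality, then the false-positive rate. For example, 0.10 × 5.29 / 0.3 = 1.76.

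The plan specifies independent t-tests, which ignore the pairing. With within-patient correlation ρ, the per-side SD is SD / √(2(1 − ρ)). At an assumed ρ of 0.5 this equals SD, so the test's standard error is SD × √(2/28), which is √2 times the true one, SD / √28. In simulation of bivariate normal data (400,000 trials per cell), a 0.10 mm lean then gives 15.6%, 4.6% and 2.4% for SDs of 0.3, 0.5 and 0.7 mm, against 0.7% with no lean. At ρ = 0.3 the rates are 27.4%, 9.9% and 5.8% (2.0% with no lean).

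**The case against.** The strongest case against is that the documents show an under-described blind and do not show a broken one.
- They do not say what the code concealed. Silence about mirroring is not proof that side was left undisguised.
- Randomisation of side means that seeing left and right is not enough. The reader must also connect a coded model to a remembered mouth, and no such recognition is documented.
- The one-examiner sentence sits next to the random choice of six models and six subjects, and may cover only the repeat readings. The caliper text names no reader.
- Each canine is measured against its own baseline position, so no direct comparison of one side with the other is described.

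All of this stands. A reader might infer that the blind cannot hold, or that the model reader certainly knew the treated side. The documents support neither. A reader might also take the 40% as the trial's false-positive rate. It is not: it belongs to a paired test on assumed inputs, and the planned test gives lower figures whenever the two sides are positively correlated.

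What remains is that the plan says blinding was ensured, and the one device it names does not ensure it if the roles overlap, as the text at face value says they do. Mirroring is also imperfect, since someone who knows a dentition well may recognise it reversed.

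**Conclusion.** The concern holds in a limited form. Coding as described is not shown to hide the treated side at the model readings. The blind fails if one person both took the weekly in-mouth readings and recognises dentitions on the models. Whether either occurred is unknown, and so is the size of any resulting bias. The calculation shows only that a lean of 0.05 to 0.10 mm could raise the paired-test error rate from 5% to between 6.5% and 40%, and that the planned independent test responds differently.

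This goes beyond a missing detail, because a better and inexpensive method exists for a primary measurement placed by eye. It should be corrected, with medium confidence. Separately, the blinding claim is worded for the whole measurement stage, but no blinding is described for the caliper.

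**What to change.** In the Blinding section, replace coding alone with the following:
1. Code the scans and, by a random list, mirror each patient's complete M0 to M3 set left-right or leave it unflipped. The whole set must go the same way so that superimposition still works. Reflection preserves distances, so displacements are unchanged.
2. Read all models in random patient order, in one batch after the last patient's M3.
3. Withhold the code, the mirroring key and the allocation record from the model reader until the readings are locked, and state by role who holds them.
4. State whether the model reader took the caliper readings or performed the perforations. Mirroring makes linking a model to a known side harder without excluding it, so this disclosure is needed too.
5. Limit the blinding claim to the model readings, and say that no blinding is described for the caliper.

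The document is written in the past tense and already reports reliability results, so the readings may be finished. In that case, re-read the stored scans in this way.

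The cost is some file handling and either deferred readings or a second reading of the models. No extra patient visit or procedure is needed.

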## **Interventions**

Before the start of orthodontic treatment, subjects were referred to the periodontal department for checking the periodontal condition and for having regular oral care. According to the inclusion criteria, all selected patients were diagnosed with class II div I malocclusion with a treatment plan including extraction of upper first premolar teeth, fixed orthodontic appliance with maximum anchorage support using miniscrews. Included subjects had their orthodontic treatment carried out by the same orthodontic resident, using fixed preadjusted edgewise-orthodontic appliances (3M Gemini Uniteks brackets; 0.022 MBT prescription). The standardized bonding method was applied according to the manufacturer instruction. Miniscrews were used to prevent unwanted tooth movement of posterior teeth during canine retraction. Therefore, after initial leveling and alignment, miniscrews (Aarhus System; American Orthodontics; 1.5 mm width and 8 mm length) were inserted also by one investigator between upper first molars and upper second premolars to be used as direct and indirect anchorage. Direct anchorage was utilized by applying the force directly from miniscrews to canines to prevent mesial movement of posterior teeth during canine retraction.

Indirect anchorage was also applied by passively ligating upper second premolars to miniscrews that might avoid mesial movement of posterior teeth especially at leveling and alignment stage of the orthodontic treatment (Figure 1).

One operator performed Atraumatic extractions of upper first premolars within the same week of miniscrew insertion. After that, leveling and alignment were accomplished until reaching the 0.019x0.025 stainless steel arch wire. The upper canine retraction was started six months after extraction to ensure the complete healing of extraction space  (Figure 2).

Occlusal interferences can decrease the rate of tooth movement  , therefore, from day 1 and during weekly follow up period, interferences were checked and if present glass ionomer cement on the lower molars were used to raise the bite.

### **Clinical Micro-osteoperforations Procedure**

MOPs were performed when the canines were ready to be retracted. The patients were asked to rinse their mouth twice by chlorhexidine for 1 minute. Local anesthesia was then given (2% lidocaine with 1:100,000 epinephrine, Septodont, France). MOPs were also performed by one investigator as judged by the randomization process either on the right or left upper canines as the following:

- a) MOP with 1.5 mm width and 3 to 4 mm depth inside the bone was applied. MOPs were performed using miniscrews (Aarhus Mini-implant system, American Orthodontics) of 1.5 mm diameter and 6 mm length in 3 points distal to canine.
- b) The points of screws insertion were demarcated by bleeding points using the calibrated periodontal probe. One row consisting of 3 holes was made distal to the canine.
- c) For standardization of the protocol, the exact location of screw insertion was determined as the following: the first dot was located 3mm distal to canine and 6 mm from the free gingival margin. The second point was marked 5 mm from the first one. The net distances between MOP after insertion of 1.5 mm diameter miniscrews were 3 mm between each

hole and 2 mm away from the contact point and 5 mm away from the free gingival margin (Figure 1).

- d) The miniscrew length of 6 mm was used to be inserted 3 to 4 mm deep into the bone and to account for the thickness of the soft tissue of about 2 to 3 mm.

After application of MOP, the extraction space was started to be closed using NiTi close coil spring connecting from the miniscrews between upper second premolar and first molar to power arm extended from the vertical slot of the upper canine bracket (3M Unitek, 9mm, 150g) (see Figure 3). The force was measured by force gauge (Correx, Dentaurum, Germany) at the day of application to ensure the constant and equal amount of force between all subjects and also between experimental and control sides.

After the intervention, the patients were instructed to take analgesics, such acetaminophen/Tylenol, only if necessary. Anti-inflammatory NSAIDs were avoided because of their known effect on tooth movement. Maintaining good oral hygiene and using chlorhexidine 0.2%, twice a day for five days, were recommended.

### **Outcomes (primary and secondary) and any changes after trial commencement**

#### **Primary Outcomes**

**The** rate of tooth movement as primary outcome was determined by indirect measurement of study models and direct intraoral measurement as the following:

Alginate impressions were taken every month and study models were fabricated. The study models were then scanned with Ceramill Map 400- scanner with an accuracy of 0.02 mm (AmannGirrbach, Koblach, Austria) to obtain the three-dimensional (3D) model. By using Ceramill Mind design (CAD: computer-aided design) software (AmannGirrbach, Koblach, Austria), 3D model measurements were obtained. The baseline 3D digital model (M0) was superimposed to 3D digital models of following months (M1: 1st month, M2: 2nd month, M3: 3rd month) to determine the anteroposterior displacement of canines. The stable reference landmark used was the rugae area as recommended by other studies . To superimpose two

3D digital models, a generic visualization mesh of the following 3D model was added to the baseline model; and then performs registration of the selected reference points at rugae area (Figure 4-A,B). The best fit matching of the superimposition was evaluated by a color map with a spectrum of colors in which blue color represented the best matching while red represented the worst (Figure 4-C). From buccolingual view, the amount of canine's displacement was measured from the most middle projection from the distal surface of upper canines in baseline model to the most middle projection from the distal surface of upper canines of superimposed transparent models (M1, M2, M3) (Figure 5-A). A reference plane parallel to the bracket slots was used to ensure the standardized orientation of all measurements from buccal view (Figure 5-C). From the occlusal view, the same point was localized at the middle of the distal surface of canines to be parallel to the line of arch anterioposteriorly (Figure 5-B). Additionally, Direct measurement of distance between canine and second premolar in the patient's mouth was done every week using digital caliper (IOS, USA), from upper mesial wing of the canine bracket to upper distal wing of second premolar bracket in both right and left sides parallel to the occlusal plane for 3 months period.

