## Figure ligands

**Figure 1:** Micro-osteoperforations protocol

**Figure 2:** Diagrams of time events during the study

**Figure 3:** Clinical Micro-osteoperforations application. A, calibrated periodontal probe to locate the point of miniscrew insertion. B, Three bleeding points. C & D, First MOP application. E, 2nd MOP application. F, Three MOP were visible distal to canines. G, canine retraction by closed coil spring.

[figure not shown]
**Figure 4:** 3D digital superimposition. A, registration of 4 reference points at medial and lateral of third rugae area. B, performing registration and best-fit matching. C, best-fit color matching with blue the best match and red the worst.

**Figure 5:** Measurement of amount of canine retraction **on** 3D digital models. A, buccal view of upper left canines showing measurement tools on the Ceramill mind software. C, occlusal view of the canines showing the measurement tool. The canines in baseline model (Yellow color) and in the 3rd month model (purple color). B, the reference plane parallel to the bracket slots.

[figure not shown]

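### The primary outcome rests on two instruments that measure different quantities, with no decisive instrument or month named, and the only masking described cannot cover one of them

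*Combined protocol and SAP*

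**What the plan says.** The Primary Outcomes section names one outcome and gives it two sources: the "rate of tooth movement as primary outcome was determined by indirect measurement of study models and direct intraoral measurement as the following".

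- **Models.** The baseline model is "superimposed to 3D digital models of following months (M1: 1st month, M2: 2nd month, M3: 3rd month"), registered on the rugae. The "displacement was measured from the most middle projection from the distal surface of upper canines in baseline model" to the same landmark on each later model. This gives three readings per side.
- **Caliper.** Direct measurement in the "mouth was done every week using digital caliper (IOS, USA"). Each reading spans the distance "from upper mesial wing of the canine bracket to upper distal wing of second premolar bracket", taken on both sides for three months.

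The section does not rank the two instruments, name a deciding month, or give a formula that turns either series into a rate. The Statistical analysis section applies independent-sample t-tests to the primary outcome, counts p ≤ 0.05 as significant, and states no order of testing. The effect size of 0.8 in the Sample size calculation section is not tied to an instrument or a month.

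The Blinding section says that patient and clinician could not be blinded. It then says that blinding was secured at data collection, and the one mechanism it gives is coding of the digital models.

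**The concern.** One named outcome yields several candidate answers. The two instruments do not estimate the same quantity, and the three model months need not agree. If they differ, no rule says which result answers the primary question, so the choice can follow the data.

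The masking gap makes the choice of instrument matter more. A model-based result rests on coded files. A caliper result is read in the mouth of a patient whose treated side cannot be hidden by coding a model, and no other safeguard is described. If the caliper result were reported as primary, the reader could not check its protection from the document.

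**Working it through.** **1. Do the instruments measure the same thing?** Let *c* be distal canine movement and *m* mesial premolar movement on one side.

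- Model reading = *c*, because the rugae are the reference.
- Fall in caliper distance = *c* + *m*, because both ends are on teeth.
- MOP minus control by model = *c*₁ − *c*₀. By caliper = (*c*₁ − *c*₀) + (*m*₁ − *m*₀).

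The two agree only if premolar movement is nil or equal on the two sides. The Interventions section uses miniscrews to limit it, so *m* may be small, but the document reports no value.

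**2. The plan's own figure.** Inputs from the Sample size calculation section: effect 0.8, alpha 0.05, power 0.90, 28 per group, 56 in total. For an independent t-test the noncentrality is 0.8 × √(28/2) = 2.99 on 54 df.

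- One-sided 5%: power 0.905, so 28 per group reproduces.
- Two-sided 5%: power 0.836, and 34 per group would be needed.

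The figure assumes a single test and does not indicate which reading that test uses. Sidedness is not stated; that is a separate matter. Each patient supplies both sides, so 28 and 56 pairs are both shown below.

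**3. How often would the two instruments give different answers?** Simulation of normal data, tested two-sided at 5% with the planned statistic t = (mean₁ − mean₀)/√((s₁² + s₀²)/n) on 2n − 2 df. Assumed, not in the documents: correlation between readings 0.5 to 0.9, correlation between sides 0 to 0.7, and the same true effect of 0.8 on both readings. The table gives the share of trials with 28 pairs in which one instrument has p ≤ 0.05 and the other does not.

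| Side-to-side correlation | Reading corr. 0.5 | 0.8 | 0.9 |
|---|---|---|---|
| 0 | 0.195 | 0.125 | 0.090 |
| 0.3 | 0.160 | 0.103 | 0.074 |
| 0.5 | 0.120 | 0.079 | 0.059 |
| 0.7 | 0.076 | 0.048 | 0.035 |

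The range is about 4% to 20%. With 56 pairs it is 0.000 to 0.021, or 0% to 2%.

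**4. Is type I error inflated?** Chance of any p ≤ 0.05 when there is no effect, 28 pairs, reading correlation 0.5 / 0.8 / 0.9:

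| Test | Two readings | Three readings |
|---|---|---|
| Paired t | 0.09 / 0.08 / 0.07 | 0.13 / 0.10 / 0.09 |
| Planned independent t, side correlation 0 | 0.091 / 0.079 / 0.070 | 0.127 / 0.099 / 0.086 |
| Planned, side correlation 0.3 | 0.037 / 0.031 / 0.028 | 0.054 / 0.041 / 0.038 |
| Planned, side correlation 0.5 | 0.013 / 0.011 / 0.010 | 0.018 / 0.015 / 0.014 |

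For independent readings the ceilings would be 1 − 0.95² = 9.75% and 1 − 0.95³ = 14.3%. The planned test ignores the pairing. With side-to-side correlation ρ, the true standard error is √(1 − ρ) times the one it uses (√0.7 = 0.84 at ρ = 0.3), so each single test is conservative. The chance of any false positive passes 5% only when ρ is below about 0.15 to 0.23 for two readings, or 0.22 to 0.32 for three. The documents do not report ρ.

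**5. Masking.** A code on a digital file hides the side from whoever measures that file. It has no counterpart for a reading taken in the mouth.

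**The case against.** **Nothing shows selection.** The end of the Secondary Outcomes section states that outcome measures did not change. That stands, and no selection is alleged. But an unranked set can stay unchanged and still leave the choice open. The caliper paragraph is introduced as an addition, which hints at a lesser role without stating one.

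**Premolar movement is controlled.** The Interventions section describes "passively ligating upper second premolars to miniscrews that might avoid mesial movement of posterior teeth", stressing the levelling stage. It also says that miniscrews and direct anchorage served to prevent posterior movement during retraction, and the coil spring runs from miniscrew to canine. This stands: the difference between the instruments may be small. It remains a difference in what is measured.

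**The numbers do not measure the harm.** Step 3 gives both instruments the same true effect, so the splits are sampling noise around a threshold, not the result of measuring different things. This is right, and the figures are illustration only.

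Three stronger readings are tempting, and the documents do not support them:

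- *The caliper readings were unmasked.* The Blinding section says that the investigator was blinded at data collection. What is missing is a mechanism that could apply to the caliper. The remark that one examiner did all measurements sits in the reliability paragraph and may describe only that exercise.
- *The viewing plane is a further open choice.* The text says that displacement was measured from the buccolingual view and then adds: "From the occlusal view, the same point was localized at the middle of the distal surface of canines". That reads as locating one point, not as a second reading. The Figure 5 legend, "C, occlusal view of the canines showing the measurement tool", is weak evidence against this: the figure is not available here, and its B and C labels are reversed relative to the text.
- *The plan as written inflates type I error.* Step 4 shows that this depends on an unreported correlation.

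**Conclusion.** The point holds. One primary outcome is defined by two instruments that capture different quantities, neither the instrument nor the month is fixed, and the stated masking mechanism can protect only one instrument. These conclusions come from the text and need no simulation.

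The size is modest and conditional. At the plan's effect of 0.8, under the assumed correlations and equal true effects, the two instruments disagree on significance in about 4% to 20% of trials with 28 pairs and 0% to 2% with 56. Correctly sized paired tests would give about a 7% to 9% chance of any false positive with two readings and 9% to 13% with three. No inflation is shown for the independent test actually planned. The change should be made, but the point does not establish that any reported result is wrong.

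**What to change.** 1. In Primary Outcomes and Statistical analysis, name one primary endpoint on the coded, rugae-superimposed models, for example buccal-view canine displacement from M0 to M3. The choice of M3 is a judgement; it covers the full three months.
2. Test it once at two-sided 5% with a paired t-test in place of the independent t-test, since each patient supplies both sides.
3. Make the other model months and the caliper series secondary, with one caliper summary per side, for example a slope in mm per week.
4. In Blinding, limit the claim to the digital-model measurements, or state how caliper readings were masked.
5. If results were already known when this is adopted, label the endpoint choice post hoc and claim no error control from it.

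**Cost.** Rewording and one re-analysis of data already collected; no new measurements. An effect seen only early or only by caliper becomes secondary evidence. The document is written in the past tense, so the gain may be limited to transparent reporting. Keeping both instruments as alternatives would cost more: with 0.025 each, the plan's own one-sided independent-test basis needs 34 per group rather than 28, and power at 28 falls to 0.836.
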